#### **11.5.5.4 Other Safety Measures**

Vital signs will be summarized descriptively, including change from baseline for continuous measures. Vital sign abnormalities will be summarized descriptively.

Abnormal findings in physical examination will be summarized descriptively.

#### **11.5.6 Immunogenicity Analysis**

All immunogenicity analyses will be performed in the PP population and select analyses will be repeated in the FAP. All descriptive analyses will be conducted across all participants within a group/time point combination, and these will be repeated for each site.

##### **11.5.6.1 Descriptive Analyses**

At each time point where NAb titers are obtained:

- Median of  $\log_2$  antibody titers will be computed along with 95% CIs
- GMT with accompanying 95% CIs will be computed. GMTs will be estimated with likelihood-based methods (SAS PROC LIFEREG) to accommodate censoring at assay ULOQ and LLOQ.
- The geometric mean fold rise (GMFR) will be computed for each post-baseline time point as the reverse-transformed difference between the post-baseline  $\log_2$  value and the baseline  $\log_2$  value and accompanied by two-sided paired-sample 95% CIs computed using asymptotic methods on the  $\log_2$  scale, then reverse-transformed. A subgroup analysis of GMFR will consider only those participants with values between the LLOQ and ULOQ (exclusive of the endpoints) for the numerator and denominator samples. For post-dose-2 GMFR, this will be computed from baseline, and from the pre-dose-2 titer. Among these participants, a plot of the  $\log_2$  fold rise vs the baseline  $\log_2$  antibody titer will be generated.
- Type-specific seroconversion rates with 95% exact CIs will be tabulated for post-vaccination time points. Seroconversion rate will be computed among those participants with seroconversion possible to observe (within 4-fold of the assay ULOQ). For post-dose-2 seroconversion, seroconversion rates will be computed both from baseline and from the pre-dose-2 titer

- In addition, the rate of any fold-rise (titer increased from baseline) and a minimum 2-fold rise in titer and accompanying CIs will be computed in the same manner
- Type-specific seroprotection rates with 95% exact CIs will be tabulated
- Plots of the reverse cumulative distribution of antibody titers will be generated

Additional figures will display immunity and changes in immunity over time, by type. Additional subgroup computations will be specified and conducted, per the SAP.

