### *Immunogenicity Evaluation*

[figure not shown]
Assessment of immunogenicity is a secondary objective in this study. Due to the prior vaccinations received by those to be enrolled into the study, baseline immunity (titer of type-specific neutralizing antibody) to poliovirus types 1 and 3 is expected to be high, with the level boosted by study vaccination. While it is expected that the presence of an immune response can be observed by an increase in neutralizing antibody titer following vaccination, and because the post-vaccination immunity is anticipated to exceed the assay upper limit of quantification (ULOQ) for some participants, definitive comparisons of study vaccination groups to the relevant control (nOPV vs type-specific control, within cohort according to prior vaccination [exclusively IPV vs OPV-containing]) will not be possible within this phase 1 study. Evaluation of immunogenicity, therefore, will be primarily descriptive in nature; comparisons to the relevant control will be made, but the sample size is not based on achieving a specific level of statistical power for these comparisons. Comparative evaluation for immunogenicity will focus on the cohorts previously receiving OPV vaccinations but will also be conducted among exclusively IPV-vaccinated participants.

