Prior studies of type 2 in OPV-vaccinated adult populations indicate baseline immunity within the quantifiable range, with mean  $\log_2$  neutralizing antibody (NAb) titers ranging from 7.8 to 8.8 (unpublished data), and with the majority of participants achieving NAb titer >ULOQ 28 days following a single dose of a Sabin-2 vaccine as well as investigational type 2 vaccines. Using a regression model permitting censoring at assay lower limit of quantification (LLOQ) and ULOQ, the standard deviation (SD) of post-vaccination NAb titers is estimated to be in the range of 3 – 3.5 on the  $\log_2$  scale, which is consistent with other published data for type 1 (prior to a boost vaccination in adulthood) [11]. In the study involving type 2, the post-vaccination GMT ratio (candidate/control) and its corresponding CI were able to be estimated; similar methods will be employed here (see below). With respect to binary immune response endpoints (seroconversion, other seroresponse rates), data from the type 2 study indicate seroconversion rates ranging from approximately 30% to 75%, depending on the vaccine and potency level administered. Rates of a minimum 2-fold response ranged from approximately 50% to 75%, with rates of any fold-rise ranging from approximately 60% to 85%.

Using these values, simulation studies were conducted to evaluate the precision of estimates of the GMT, GMT ratio, response rates, and differences in response rates, assuming that 48 and 24 of the 50 and 25 or 28 and 14 of the 30 and 15 prior OPV participants randomized to receive nOPV or mOPV, respectively, provide samples for analysis. The figure below displays the average half-width of the two-sided 95% confidence intervals for the four evaluations across the range of relevant inputs ( $\log_2$  NAb SD for GMts, true rate for the various response rates). The level of precision expected to be available, described within the figures, is considered adequate to determine if there is sufficient evidence of an immune response to warrant progressing into populations where the immune response may be more thoroughly described and compared.

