#### **11.5.6.2 Comparative Analyses**

No specific immunogenicity hypothesis is to be tested. Descriptive comparative evaluation will be conducted with multiple endpoints; such evaluations will be conducted for the nOPV-vaccinated groups compared to the mOPV-vaccinated control groups within type, and within background vaccination cohort (within groups defined by exclusive IPV prior vaccination, and separately among those previously receiving OPV). Separately for each pairwise comparison, the NAb GMT ratio (nOPV/mOPV) will be estimated via a linear model of the  $\log_2$  NAb titer as a function of group with a fixed parameter for site and a covariate for the  $\log_2$  NAb titer level. This will be conducted using SAS PROC LIFEREG to account for censoring of the dependent variable assuming a Normal error distribution on the  $\log_2$  scale; baseline values achieving ULOQ or LLOQ will be replaced with ULOQ or LLOQ, as appropriate, for the covariate. The log-scale difference and its corresponding confidence interval, estimated with SAS LSMEANS, will be reverse-transformed to obtain the estimated GMT ratio and corresponding 95% confidence interval. Among the subset of participants where baseline and post-baseline NAb titers are below the assay ULOQ, the fold-rise in titer will be computed, and these fold-rises will be compared between nOPV vs mOPV groups within background vaccination cohort and type using standard *t*-distribution methodology.

Similar comparisons will be made for seroprotection rates, seroconversion rates, and other response rates (any fold-rise, 2-fold rise). For these binary variables, two-sided 95% Miettinen and Nurminen confidence intervals for the rate difference (nOPV minus mOPV) will be computed, and these will be supplemented with a two-sided Fisher exact test p-value.

Imbalance in baseline immunity between sites will be evaluated via the Kruskal-Wallis test for Nab titers. Wherever the global test is significant at two-sided level  $\alpha = 0.10$ , pairwise comparisons will be drawn from the Wilcoxon test.

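### The all-participant fold rise (GMFR) in 11.5.6.1 ignores censoring at the assay limits, which the GMT beside it accounts for, so it can be biased and disagree with the GMTs

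*Protocol*

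**What the plan says.** Section 11.5.6.1 lists the descriptive immunogenicity summaries.

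- For the GMT: "GMTs will be estimated with likelihood-based methods (SAS PROC LIFEREG) to accommodate censoring at assay ULOQ and LLOQ".
- For the fold rise: "The geometric mean fold rise (GMFR) will be computed for each post-baseline time point as the reverse-transformed difference between the post-baseline" and baseline log2 values, "accompanied by two-sided paired-sample 95% CIs computed using asymptotic methods on the" log2 scale. For dose 2 it is computed both from baseline and from the pre-dose-2 titer.
- The only mention of assay limits for the fold rise is a restricted analysis: "A subgroup analysis of GMFR will consider only those participants with values between the LLOQ and ULOQ (exclusive of the endpoints").

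In section 11.5.6.2 the GMT ratio is again fitted with PROC LIFEREG. Substitution at the limit is written down only for the baseline covariate: "baseline values achieving ULOQ or LLOQ will be replaced with ULOQ or LLOQ, as appropriate, for the covariate".

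On how often the ULOQ will be reached, section 11.3 makes two statements. For this trial: "because the post-vaccination immunity is anticipated to exceed the assay upper limit of quantification (ULOQ) for some participants". For earlier type 2 studies in OPV-vaccinated adults: "with the majority of participants achieving NAb titer >ULOQ 28 days following a single dose of a Sabin-2 vaccine". The same paragraph gives mean baseline log2 "titers ranging from 7.8 to 8.8 (unpublished data") and a post-vaccination log2 SD of 3 to 3.5. The ULOQ, the share above it, the baseline SD and the correlation between the two titers are not stated.

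**The concern.** A participant whose post-dose titer exceeds the ULOQ has no observed fold rise. If the baseline is quantifiable, the data give only a minimum for the rise. If the baseline is capped and the later titer is not, they give only a maximum. A plain paired difference needs a number for each titer. Pairs at the limits are removed only in the subgroup, so the main GMFR must include them, presumably scored at the limit. The interval then measures the spread of capped differences and is centred on the wrong value.

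Two summaries in the same list would handle the same titers under incompatible assumptions, so the GMFR would not match the ratio of the Day 29 and baseline GMTs. The dose-2 rise from the pre-dose-2 titer suffers most. A participant above the ULOQ at both samples scores exactly no rise, so a small reading cannot separate a weak boost from assay saturation.

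**Working it through.** **The plan's own figures.** No GMFR figure is stated. Section 11.3 does give interval half-widths for the difference in mean log2 titer: 1.48 and 1.92 (SD 3.0, at 48:24 and 28:14), and 0.97 and 1.25 (SD 2.0, same group sizes). The formula 1.96 × SD × √(1/n1 + 1/n2) gives 1.470, 1.925, 0.980 and 1.283, all within 3%. The SD and sample-size inputs are therefore understood as the plan uses them.

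**Inputs.** From section 11.3: baseline mean 7.8–8.8, post-dose SD 3–3.5, 48 or 28 evaluable in the nOPV group and 24 or 14 in the mOPV group. Assumed: normal log2 titers, ULOQ at log2 10–11, LLOQ at log2 2.5, baseline SD 2–3.5, correlation 0.5, and share p above the ULOQ after dosing of 20–70%.

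**Step 1, cap on the post-dose titer only.** Capping a normal variable at the point exceeded by a share p lowers its mean by SD × [φ(k) − k·p], with k = z(1−p). This does not depend on where the ULOQ lies.

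| p | Shift, SD 3 to 3.5 (log2) | GMFR low by |
|---|---|---|
| 30% | 0.57–0.67 | 1.5–1.6-fold |
| 50% | 1.20–1.40 | 2.3–2.6-fold |
| 60% | 1.62–1.88 | 3.1–3.7-fold |
| 70% | 2.14–2.50 | 4.4–5.7-fold |

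**Step 2, offset from a capped baseline.** Take baseline mean 8.3, SD 3, ULOQ 10.5. Then k = 2.2/3 = 0.733, the share above is 0.232, and the shift is 3 × (0.305 − 0.733 × 0.232) = 0.40. At p = 50% the net shift is 1.20 − 0.40 = 0.80 log2, about 1.7-fold. Simulation of this case at n = 48 gave a true rise of 2.20 log2, a planned estimate of 1.42 (1.72-fold low) and 33% coverage of the 95% interval.

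**Step 3, both samples capped, all assumed inputs varied, n = 48 and 28.** These ranges include a post-dose SD of 2 as a sensitivity case.

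| p | GMFR low by | Coverage |
|---|---|---|
| 30% | 0.85–1.44-fold | 61–94% |
| 50% | 1.4–2.4-fold | 1–73% |
| 60% | 1.7–3.4-fold | 0–32% |
| 70% | 2.1–5.3-fold | 0–4% |

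With the SD held to the plan's 3–3.5, a rerun moves the lower end at 60% to 1.9-fold and at 70% to 2.8-fold, and leaves 50% at 1.4–2.4. The reversed values at 30% (below 1) arise where the assumed post-dose mean lies below the baseline mean. At n = 14 (baseline 8.3, SD 3 at both samples, ULOQ 10.5), coverage is 66%, 46% and 21% at 50%, 60% and 70%.

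**Step 4, the quantifiable-pairs subgroup.** It keeps only participants who stayed below the ULOQ after dosing. It is low by about 1.3–3.3-fold at 50% and 1.5–4.4-fold at 60%.

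**Step 5, dose 2 from the pre-dose-2 titer (SD 3).** Capped means come from the Step 1 formula.
- Pre-dose-2 mean at the ULOQ (50% capped): capped mean ULOQ − 1.20. A true 2-fold boost gives ULOQ − 0.76, so the rise reads 0.43 log2, or 1.35-fold. A true 4-fold boost gives ULOQ − 0.45 and reads 0.74 log2, about 1.7-fold.
- Pre-dose-2 mean one log2 above the ULOQ (63% capped): the same boosts read about 1.24-fold and 1.4-fold.

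**Step 6, the remedy.** Difference of censored-normal means in the same simulated participants, with a standard error that keeps the pairing (n = 48, baseline 8.3, SD 3 at both samples, ULOQ 10.5, 200 trials per row):

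| p | True log2 rise | Planned (coverage) | Censored (coverage) |
|---|---|---|---|
| 50% | 2.20 | 1.42 (33%) | 2.28 (92%) |
| 60% | 2.96 | 1.70 (4%) | 2.94 (95%) |
| 70% | 3.77 | 2.01 (0%) | 3.66 (95%) |

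At n = 14 the censored estimate still covers 94–97%, with a median 1.08- to 1.15-fold low.

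**The case against.** The best defence is that little hangs on this number. GMFR is not among the endpoints in section 2.3.2, which lists medians, GMTs, adjusted GMT ratios and fold-rise frequencies. It is also not among the quantities whose precision section 11.3 examines. Section 11.5.6.2 tests no immunogenicity hypothesis, and no between-vaccine comparison of the all-participant GMFR is specified: the fold-rise comparison there uses participants below the ULOQ. Censoring-adjusted GMTs appear at each time point, so a reader could form a better ratio. An understated rise is conservative for showing a response. Scoring capped values at the limit is inferred for the GMFR, and section 11.5.1 leaves further detail to the SAP.

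Most of this stands and limits the consequence. It does not clear the estimator. The protocol already states a paired difference and an asymptotic paired interval, and confines the removal of capped pairs to a subgroup, so this is a chosen method and not detail left open.

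A reader might infer that the plan expects most titers in this trial to exceed the ULOQ, so that the interval would almost never cover the truth. The documents do not support that. Section 11.3 says some participants; the majority refers to earlier type 2 studies in OPV-vaccinated adults and says nothing about the exclusive-IPV cohorts. With 20% above the ULOQ (baseline 8.3, SD 2.5, correlation 0.6, ULOQ 10.5, n = 48) the bias is only 1.05- to 1.09-fold and coverage 93–94%.

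**Conclusion.** The point holds, conditionally on size. The all-participant GMFR is inconsistent with the GMT and GMT ratio in the same plan, and the subgroup does not repair it. If the share above the ULOQ resembles the earlier type 2 experience, the understatement is material: about 1.4- to 2.4-fold at 50% and 1.7- to 3.4-fold at 60%, with coverage of 1–73% and 0–32%. At 30% it is 1.44-fold or less and can be slightly reversed. These figures rest on normal log2 titers and on assumed values for the ULOQ, baseline SD and correlation. The dose-2 rise from the pre-dose-2 titer is the most exposed.

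It would be too strong to say that the decision to proceed to children rests on GMFR, or that the error distorts the planned nOPV versus mOPV comparison. The protocol specifies neither. The consequence is a descriptive fold rise and interval that can mislead and that will disagree with the censored GMTs beside it. It should be corrected, but it threatens no listed endpoint.

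**What to change.** In 11.5.6.1, define the all-participant GMFR, both from baseline and from the pre-dose-2 titer, as the back-transformed difference of the LIFEREG censored means at the two time points. Use the same participants at both, and take the interval from a bootstrap that resamples participants so that the pairing is kept. Report the share of titers at the ULOQ by group and time point.

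If the simple paired difference is kept, label it as affected by capping at the assay limits. Do not call it a lower bound: a capped baseline pushes the rise the other way. Keep the quantifiable-pairs subgroup only as a description of those participants.

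The cost is a change of wording and a small amount of code around a procedure the plan already uses. The price is reliance on the normal model already accepted for the GMT, and a wider interval. The check above used an analytic standard error, so the bootstrap should be tried at the smallest group sizes before it is fixed.

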#### **11.5.6.2 Comparative Analyses**

No specific immunogenicity hypothesis is to be tested. Descriptive comparative evaluation will be conducted with multiple endpoints; such evaluations will be conducted for the nOPV-vaccinated groups compared to the mOPV-vaccinated control groups within type, and within background vaccination cohort (within groups defined by exclusive IPV prior vaccination, and separately among those previously receiving OPV). Separately for each pairwise comparison, the NAb GMT ratio (nOPV/mOPV) will be estimated via a linear model of the  $\log_2$  NAb titer as a function of group with a fixed parameter for site and a covariate for the  $\log_2$  NAb titer level. This will be conducted using SAS PROC LIFEREG to account for censoring of the dependent variable assuming a Normal error distribution on the  $\log_2$  scale; baseline values achieving ULOQ or LLOQ will be replaced with ULOQ or LLOQ, as appropriate, for the covariate. The log-scale difference and its corresponding confidence interval, estimated with SAS LSMEANS, will be reverse-transformed to obtain the estimated GMT ratio and corresponding 95% confidence interval. Among the subset of participants where baseline and post-baseline NAb titers are below the assay ULOQ, the fold-rise in titer will be computed, and these fold-rises will be compared between nOPV vs mOPV groups within background vaccination cohort and type using standard *t*-distribution methodology.

Similar comparisons will be made for seroprotection rates, seroconversion rates, and other response rates (any fold-rise, 2-fold rise). For these binary variables, two-sided 95% Miettinen and Nurminen confidence intervals for the rate difference (nOPV minus mOPV) will be computed, and these will be supplemented with a two-sided Fisher exact test p-value.

Imbalance in baseline immunity between sites will be evaluated via the Kruskal-Wallis test for Nab titers. Wherever the global test is significant at two-sided level  $\alpha = 0.10$ , pairwise comparisons will be drawn from the Wilcoxon test.

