The figure indicates, for example, that if the SD of the  $\log_2$  post-baseline serum NAbs is 3.0 and both candidate and control vaccines are equally immunogenic, then one can expect, on average, that the CI for the difference in mean  $\log_2$  NAbs will be approximately (-1.48, 1.48) with 48:24 or (-1.92, 1.92) with 28:14 when the estimated difference is 0 (ratio = 1), providing high confidence that the actual absolute  $\log_2$  difference is <2 (ratio <4). If instead the SD is 2.0, the CI would be approximately (-0.97, 0.97) with 48:24, providing confidence that the actual absolute difference is <1 (ratio <2). For the lower sample size, with an SD of 2.0, the CI would be approximately (-1.25, 1.25), providing high confidence that the actual absolute  $\log_2$  difference is <1.58 (ratio <3). For the candidate vaccine group alone, assuming a SD just less than 3.5 and 48 evaluable subjects, the CI for the mean  $\log_2$  titer would be approximately  $\pm 1.0 \log_2$ . That is, if the estimated GMT is  $2^8$  (256), the figure indicates the CI would be expected to be approximately ( $2^7$ ,  $2^9$ ), or equivalently (128, 512), on average. If instead the SD is 2.5 with 48 evaluable subjects, the CI would be expected to be approximately ( $2^{7.3}$ ,  $2^{8.7}$ ), or equivalently (158, 416), on average.

With respect to response rates, for which precision is naturally lower than the continuous measurement of serum NAbs: if a true response rate is 50% in each group (maximum variability), then the CI for the estimated candidate vaccine response rate would be expected to average  $\pm 15\%$  ( $\pm 20\%$  for 28 evaluable subjects) from the point estimate, and the CI for the difference in response rates would be expected to average  $\pm 23\%$  ( $\pm 30\%$  for 28:14) from the point estimate.

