### *Intestinal Immunity, Genetic Stability*

In recognition that previously OPV-vaccinated participants are unlikely to shed vaccine virus in substantial quantities, the 30-40 participants for each type with exclusive prior IPV vaccination to be randomized 1:1 to nOPV or mOPV are included primarily to provide a preliminary indication of intestinal take (shedding of virus, indicating replicating infection), as well as to provide samples for potential genetic stability analysis of shed virus, including NGS and evaluation in a mouse neurovirulence assay. The relevant

neurovirulence assay for comparison to Sabin-strain vaccines is yet to be developed, but it is anticipated that a null hypothesis of no difference, vs. an alternative hypothesis of superiority of nOPV to mOPV will be evaluated from this model; a defined level of statistical power is not a requirement for this preliminary evaluation. It is currently unknown what levels of paralysis may be seen in transgenic mice in such an assay as assay development is ongoing but based on preclinical data indicating no paralysis associated with passaged candidate vaccine virus, and the known reversion to neurovirulence resulting in frequent paralysis of mice inoculated with reverted Sabin-strain vaccines, sufficient discriminatory capability is expected to be provided by 15-20 participants per vaccine.

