### **11.5 Analytical Methodology**

#### **11.5.1 Descriptive Methodology**

All data collected will be summarized and/or listed. Analyses will be performed using SAS® software (SAS Institute Inc., Cary, NC, USA) version 9.4 or higher.

Unless otherwise specified, descriptive statistics include the mean, SD, median, minimum, maximum for continuous variables, and the number and proportion in each group for categorical variables. Unless otherwise specified here or in the SAP, statistical tests, and confidence intervals (CIs) will be computed using a two-sided 5% significance level. Exact (Clopper-Pearson) CIs will be used for univariate summaries of dichotomous variables, and Miettinen-Nurminen score-based confidence intervals will be used for rate differences. All proportions will use as denominator the number of participants contributing data at the specified time point within the specified group and study population.

Summaries will be presented by group and by time point, where relevant.

For all summaries outlined below, the SAP will contain additional detailed description of the analyses to be conducted.

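### The 95% intervals for GMTs and GMT ratios come from a censored maximum-likelihood fit with no small-sample correction, so at this trial's cohort sizes they are moderately too short (about 91–94% coverage)

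*Protocol*

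**What the plan says.** Section 11.5.1 sets the level: "confidence intervals (CIs) will be computed using a two-sided 5% significance level". Section 11.5.6.1 gives the single-group method: "GMTs will be estimated with likelihood-based methods (SAS PROC LIFEREG) to accommodate censoring at assay ULOQ and LLOQ".

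For the group comparison, Section 11.5.6.2 models log2 titer "as a function of group with a fixed parameter for site and a covariate for the" baseline log2 titer, and adds: "This will be conducted using SAS PROC LIFEREG to account for censoring of the dependent variable assuming a Normal error distribution". The interval is then taken from that fit: "The log-scale difference and its corresponding confidence interval, estimated with SAS LSMEANS, will be reverse-transformed to obtain the estimated GMT ratio". Neither section mentions a t quantile or a degrees-of-freedom correction for these intervals. The fold-rise comparison in Section 11.5.6.2 does use Student t methods.

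Section 11.3 reports average half-widths from simulation, "assuming that 48 and 24 of the 50 and 25 or 28 and 14 of the 30 and 15 prior OPV participants randomized". For the difference in mean log2 titer it prints 0.97 (48:24) and 1.25 (28:14) at SD 2.0, and 1.48 and 1.92 at SD 3.0. The 1.25 reads: "For the lower sample size, with an SD of 2.0, the CI would be approximately (-1.25, 1.25". The exclusively-IPV cohorts are smaller: "the 30-40 participants for each type with exclusive prior IPV vaccination to be randomized 1:1 to nOPV or mOPV".

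**The concern.** Two features of a likelihood interval shorten it in small samples. The residual SD is estimated with divisor n where an unbiased variance needs n−p, with p the number of mean parameters. The Wald interval then uses 1.96 where a t quantile is needed. In hundreds of participants neither matters. Here a comparison rests on 30 to 75 people, with parameters for group, baseline titer and each site.

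At stake is the accuracy of the 95% label on a listed secondary endpoint, the baseline-adjusted GMT ratio. No immunogenicity hypothesis is tested, so the interval is how a reader will judge uncertainty. The fold-rise result in the same section would also stand on a different footing. Finally, Section 11.3 draws statements about detectable ratios from these widths.

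**Working it through.** **Inputs.** Level, estimator, model terms, sample sizes and printed half-widths are from Sections 11.3, 11.5.1 and 11.5.6. Assumptions, because the protocol does not give them: the number of sites; ULOQ and LLOQ (10.5 and 2.5 on the log2 scale); the censored fraction (0–50%); a baseline-to-post correlation of 0.5; and 14:14 or 19:19 evaluable in the IPV cohorts.

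**1. The plan's own half-widths.** Let r = sqrt(1/n1 + 1/n2), which is 0.2500 for 48:24 and 0.3273 for 28:14. Let c = E[s]/σ, which is 0.9964 on 70 df and 0.9938 on 40 df. With two mean parameters and no censoring:

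- ML with z: 1.960 × σ × c × sqrt((n−2)/n) × r. For 28:14 at SD 2.0: 1.960 × 2.0 × 0.9938 × sqrt(40/42) × 0.3273 = 1.244.
- Student t: t(0.975, n−2) × σ × c × r. For the same case: 2.021 × 2.0 × 0.9938 × 0.3273 = 1.315.
- Known SD with z: 1.960 × σ × r = 1.283.

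| Case | Printed | ML with z | Known SD | t | Printed / t |
|---|---|---|---|---|---|
| SD 2.0, 48:24 | 0.97 | 0.963 | 0.980 | 0.994 | 0.976 |
| SD 2.0, 28:14 | 1.25 | 1.244 | 1.283 | 1.315 | 0.951 |
| SD 3.0, 48:24 | 1.48 | 1.444 | 1.470 | 1.490 | 0.993 |
| SD 3.0, 28:14 | 1.92 | 1.867 | 1.925 | 1.972 | 0.974 |

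The printed values exceed ML with z by under 1% at SD 2.0 and by 2.5–3% at SD 3.0, by nearly the same proportion at both sample sizes. Censoring would produce that pattern. Simulated ML intervals with about 7% censored give 0.969 and 1.260 at SD 2.0. With about 16% censored they give 1.484 and 1.932 at SD 3.0. The ratio to t falls as n falls, as expected when a small-sample correction is absent.

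**2. Coverage without censoring.** Exactly, coverage = P(|t on n−p df| < 1.96 × sqrt((n−p)/n)), with p = sites + 2 (intercept, group, baseline, sites − 1). Example, 15:15 with 4 sites: p = 6, df = 24, 1.96 × sqrt(24/30) = 1.753, coverage 90.8%.

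| Arms | 1 site | 2 sites | 4 sites |
|---|---|---|---|
| 48:24 | 94.1% | 93.9% | 93.5% |
| 28:14 | 93.4% | 93.0% | 92.2% |
| 20:20 | 93.3% | 92.9% | 92.0% |
| 15:15 | 92.6% | 92.0% | 90.8% |

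Single-group GMT (p = 1): 91.9% at n = 14, 92.9% at n = 20, 93.5% at n = 28, 94.2% at n = 48.

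**3. Coverage with censoring.** Simulated ML fits with the baseline covariate, SD 3.0, about 0, 20 and 50% censored, and 1, 3 or 6 sites (3,000 runs per cell, standard error about 0.5 points) give: 48:24, 93.0–94.5%; 28:14, 91.1–93.9%; 19:19, 90.6–94.3%; 14:14, 89.2–93.9%. Values below 90% occur only at 14:14 with six sites.

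**4. Effect of a correction.** Using t on n−p df and multiplying the standard error by sqrt(n/(n−p)) brings simulated coverage to about 94–97%. The widening factor is (t/1.96) × sqrt(n/(n−p)): 1.048 and 1.064 at 48:24 with 2 and 4 sites, and (2.064/1.96) × sqrt(30/24) = 1.177 at 15:15 with 4 sites. With p = 2 it is 1.032 (48:24) and 1.057 (28:14), so the printed values rescale as 0.97 → 1.00, 1.25 → 1.32, 1.48 → 1.53 and 1.92 → 2.03.

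**The case against.** **The intervals are descriptive.** Section 11.3 says definitive comparisons are not possible in this study, and Section 11.5.6.2 tests no immunogenicity hypothesis. This stands and limits the impact. It does not make a 92% interval a 95% one.

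**The quantile is SAP detail.** The protocol names neither quantile nor degrees of freedom, and a SAP could supply a correction. But the protocol does fix the procedure and the source of the interval, and its own SD 2.0 half-widths match ML with a normal quantile.

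**A reader might infer that no valid 95% interval gives the printed half-widths.** The documents do not support that for all four. Only 1.25 at 28:14 is clearly low. At 48:24 and SD 2.0 the gap to t is 2–3%, in text offered as approximate. At SD 3.0 the printed 1.48 exceeds the known-SD 1.470 and 1.92 is almost equal to 1.925, so those figures do not show the problem by themselves. Falling below the known-SD value is also weak evidence, since Section 11.3 reports average half-widths and an unbiased SD with z averages 0.977 and 1.275 at SD 2.0.

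**Baseline adjustment offsets the loss of width.** With an assumed correlation of 0.5 the residual SD falls to 0.866σ, and 28:14 at SD 2.0 gives about 0.866 × 1.315 = 1.14 with t. So the precision actually achieved may be better than printed. Coverage is unaffected, because the adjustment shortens corrected and uncorrected intervals alike.

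**The worst figures come from the smallest cohorts.** Section 11.3 puts the comparative focus on the OPV cohorts, where uncensored coverage is 92.2–93.9% for 2–4 sites. That stands.

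**Conclusion.** The point holds at moderate size. As specified, the GMT-ratio intervals cover about 93.5–93.9% at 48:24 and 92.2–93.0% at 28:14, falling to 90.8–92.0% at 15:15. Single-group GMT intervals cover about 92–94% for n = 14 to 48. With 0–50% of titers censored, simulation gives about 90–95%, dipping to 89% only in the smallest cohort with six sites.

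The ranges for the ratio rest on an assumed 2–4 sites; even one site gives 92.6% at 15:15. The normal quantile is inferred from the likelihood method and supported by the printed half-widths.

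A reader might infer that Section 11.3's case for adequate precision fails. It does not. Uncensored average t half-widths of 0.99, 1.31 and 1.97 still satisfy its three readings (log2 difference below 1, 1.58 and 2). After rescaling the printed, apparently censored values, two become borderline: 1.00 against 1 (SD 2.0, 48:24) and 2.03 against 2 (SD 3.0, 28:14). The primary safety endpoints are unaffected.

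**What to change.** - Keep the censored-normal model. In Section 11.5.6, or in the SAP with a reference to it, state that GMT and GMT-ratio intervals use a t quantile on n−p degrees of freedom and the LIFEREG standard error multiplied by sqrt(n/(n−p)). This is exact only without censoring, and slightly conservative under heavy censoring in the smallest cohorts. Profile likelihood or bootstrap intervals are alternatives; their coverage was not checked here.
- Rerun the Section 11.3 simulation with the chosen interval and restate the average half-widths. As a guide, without censoring or covariates the t averages are about 0.99 (48:24) and 1.31 (28:14) at SD 2.0, and 1.49 and 1.97 at SD 3.0.
- Recheck the statements that the ratio is below 4 (SD 3.0, 28:14) and below 2 (SD 2.0, 48:24), and soften them if they no longer hold.

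Cost: one sentence, one line of post-processing and a rerun of an existing simulation, with no new data. Intervals become about 5–6% wider at 48:24 and up to about 18% wider at 15:15 with four sites.
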